Sponsor	
St Georges University Hospitals NHS Foundation Trust
 
SPONSOR REPRESENTATIVE: Name: [name], Head of Research Governance and Delivery
 
SPONSOR CONTACT: Name: [name] Address: St George's Joint Research Enterprise Service, [name], St George's, University of London and St George's University Hospitals NHS Foundation Trust, [name] Email: [contact] [contact]

Funder(s)	This study is funded by the Gas Safety Trust

STUDY SUMMARY	
Study Title	Cognitive, behavioural and blood biomarker assessment after carbon monoxide (CO) exposure
Internal ref. no. (or short title)	Cognitive and blood biomarker assessment after CO Exposure
Study Design	Cohort observational
Study Participants	
Individuals with proven raised levels of carboxyhaemoglobin (COHb) (>1.6% in non-smokers and >6.3% in smokers) or proven exposure to CO
 
Exclusion criteria:
 
 • age <18 years • other significant neurological condition • smoke inhalation
Planned Size of Sample (if applicable)	50
Follow up duration (if applicable)	NA
Planned Study Period	18 months
Research Question/Aim(s)	(1) To determine whether blood biomarkers sensitive to neuronal injury are elevated in the sub-acute to chronic period following confirmed environmental, non-fire

	
related exposure to CO.
 
(2) Establish whether the prevalence of neurological, cognitive and behavioural deficits associated with CO exposure can be estimated;
 
(3) Develop a sensitive and specific neurocognitive testing battery for CO poisoning
 
(4) Characterize the neurological, cognitive and behavioural impairments following a confirmed CO poisoning event

--	---

FUNDING AND SUPPORT

FUNDER(S)	FINANCIAL AND NON FINANCIAL SUPPORT GIVEN
Gas Safety Trust [name] [contact] Email: [contact]	Providing financial support for the study. Also providing support regarding dissemination of findings

ROLES AND RESPONSIBILITIES OF STUDY MANAGEMENT COMMITTEES/GROUPS & INDIVIDUALS

Trial Steering Group:

Membership will consist of personnel involved in daily operational issues in the management of the study and will act upon advice/recommendations received by the sponsor.

Trial Steering Group	
Chair	[name], Neurology Consultant, Atkinson Morley Wing St George's University Hospitals NHS Foundation Trust, [name]

1 BACKGROUND

Carbon monoxide is estimated to cause around 30 deaths^[1], 200 admissions^[2] and 4000 presentations to Emergency Departments (EDs) each year in the UK^[3]. In the longer term, CO poisoning is recognised to cause persistent neurological problems (including impairments of thinking and behavioural changes), which can develop days to weeks after the initial exposure^[4]. However, the incidence of these long-term sequelae is unknown^[4]. In addition, there is evidence of long-lasting inflammatory changes in the brain and on-going brain cell injury, although how long this persists is also unknown^[5]. One long-term follow up study 33 years after a large CO poisoning mining accident showed over 70% of those affected had evidence of cerebral atrophy (loss of brain volume)^[6], which may suggest evidence of persistent brain cell injury.

Initial assessments of CO exposure can be unreliable if blood tests are not carried out within a relatively short period after the exposure^[7] and other biomarkers (such as imaging^[8]) are insensitive to detecting previous CO exposure. Furthermore, chronic low-level exposure to CO poisoning can cause significant neurological deficits even with relatively low CO blood levels^[9].

Certain proteins that are found in brain cells can be detected in the blood of individuals following brain injury and brain cell death. These proteins have been found to be raised in the acute period after minor head injury^[10], persistently raised in patients with a traumatic brain injury and evidence of on going neurodegeneration (i.e. on going brain cell death)^[11] and in patients with various types of dementia^[12].

We will assess the presence of these proteins in the blood of 50 patients with proven CO exposure in the sub-acute to chronic timescale (2 weeks to 2 years). This has not been done before and will allow assessment of the presence of on going brain injury in these patients. We will also assess cognitive (e.g. memory, attention and speed of thinking) and behavioural impairments in these patients to help characterise the common impairments suffered following CO exposure.

2 RATIONALE

2.1 Primary aim:

To determine whether blood biomarkers sensitive to neuronal injury are elevated in the sub-acute to chronic period following confirmed environmental, non-fire related exposure to CO.

2.2 Secondary aims:

- Establish whether the prevalence of neurological, cognitive and behavioural deficits associated with CO exposure can be estimated;
- Develop a sensitive and specific neurocognitive testing battery for CO poisoning
- Characterize the neurological, cognitive and behavioural impairments following a confirmed CO poisoning event

Cognitive and blood biomarker assessment after CO Exposure

Current methods for detecting neurological injury due to CO exposure are unreliable yet the importance of neurocognitive changes found in people who have suffered from CO exposure are well depicted in case study reports^[13]. There is therefore a need to identify those patients with chronic neurological problems due to CO exposure.

Measurements of certain proteins in the blood (in particular neurofilament light (NFL)) have become increasingly sensitive over recent years to detect the presence of injury to brain cells. These proteins are present inside brain cells and if the brain cells are injured they are released into the blood. These proteins have been found to be raised in the acute period after minor head injury^[10], persistently raised in patients with a traumatic brain injury and evidence of on going neurodegeneration^[11] and in patients with dementia^[12]. Determining whether these blood biomarkers are raised following CO exposure is therefore important in order to be able to establish whether there is evidence of persistent brain injury in the sub-acute to chronic time frame after CO exposure.

Currently, it can be hard to determine whether an individual has had CO exposure as COHb levels rapidly normalise and if not taken quickly following exposure will be normal. It is therefore important to determine whether there are key cognitive and/or behavioural impairments following CO exposure and how best to measure them.

3 THEORETICAL FRAMEWORK

We will assess patients with proven exposure to CO in the sub-acute to chronic time period (2 weeks to 2 years after exposure). This will allow assessment of the use of blood biomarkers in this cohort that could be used in future patients with suspected but not proven CO exposure.

We will also use a cognitive testing battery that is validated in traumatic brain injury patients and will determine whether it is useful at characterising a profile of cognitive impairment following CO exposure.

4 RESEARCH QUESTION/AIM(S)

4.1 Primary aim:

To determine whether blood biomarkers sensitive to neuronal injury are elevated in the sub-acute to chronic period following confirmed environmental, non-fire related exposure to CO.

4.2 Secondary aims:

- Establish whether the prevalence of neurological, cognitive and behavioural deficits associated with CO exposure can be estimated;
- Develop a sensitive and specific neurocognitive testing battery for CO poisoning

Cognitive and blood biomarker assessment after CO Exposure

- Characterize the neurological, cognitive and behavioural impairments following a confirmed CO poisoning event

4.3 Outcomes:

Blood biomarker levels in patients with proven CO exposure.

Cognitive and behavioural profiles of patients with proven CO exposure

5 STUDY DESIGN and METHODS of DATA COLLECTION AND DATA ANALYSIS

The study will take place at St George's Hospital.

5.1 Methods:

A prospective observational study of patients with confirmed CO exposure. All patients will be fully assessed with a full neurological assessment and examination, a detailed battery of cognitive tests, behavioural questionnaires and blood biomarkers sensitive to persistent neuronal (brain) injury:

- The study will use Cogniclinic, a set of brief computerised cognitive tests that can be undertaken on a tablet computer which have been validated in other forms of acquired brain injuries including traumatic brain injury. This form of cognitive assessment benefits from the fact that it is easy to use and can be used in any setting. The App is free and was developed by researchers at Imperial College, London
(https://quicktech.imperialinnovations.co.uk/i/software_apps/cognitron.html)
- Patients will also complete a full set of validated behavioural questionnaires that assess quality of life, depressive symptoms, anxiety levels, post-traumatic stress symptoms, fatigue, apathy, return to work and a newly developed questionnaire that will aim to identify the presence of common post-CO exposure symptoms.
- Two 4ml samples will be taken which will be sent to the UK Dementia Research Institute at UCL ([name]'s Group) to test for neurological blood biomarkers. Research blood sample bottles will be labelled with a unique study identifier and processed according to study laboratory procedures. Blood samples will be sent to measure levels of protein biomarkers sensitive to neuronal injury. Neurofilament light (NfL) is a sensitive blood biomarker of persistent brain injury and neuronal loss. Increased levels are observed in a variety of neurodegenerative diseases, including Alzheimer's disease and motor neuron disease. Levels also remain elevated in the chronic phase after a traumatic brain injury in some individuals and relate to evidence of progressive brain atrophy (shrinkage). This may be relevant after CO exposure as some patients have progressive symptoms and it is a possible risk factor for the development of dementia. Blood biomarkers will include NfL, tau and glial fibrillary acidic protein.

Cognitive and blood biomarker assessment after CO Exposure

Once enrolled, participants will be given a unique study identifier that will be used for all data collection, tests and blood samples. All data will be stored on a password-protected database on the Hospital's servers accessible to just members of the research team. Statistical analysis will be conducted using SPSS and R. Data analysis will take place at St George's hospital and with members of the research team based at St George's University of London. The unique study identifier will be linked to the individuals' personal data on a separate password-protected database held on the Hospital's servers.

Cognitive tests and questionnaires will be compared to those from large normative control databases to identify differences between the study group (participants exposed to CO) and healthy controls. Blood tests will also be compared to a database of healthy controls to identify changes in these biomarkers after CO exposure.

The relationship between the blood biomarkers and cognitive tests/behavioural questionnaires will also be analysed to see whether there is a correlation between cognitive/behavioural impairments and evidence of brain cell injury as identified by the blood biomarkers.

Data collected from the cognitive tests and the questionnaires will be transcribed onto the main study database as soon after completion as possible. All results will be ascribed to the participants study identifier and no personal identifiable data will be included in the results database. Paper copies of the questionnaires will be kept with the participant files in a locked filing cabinet in a locked room. The blood samples will be sent as a batch with only the unique study identifier at the end of the study for analysis. No personal identifiable data will be sent with the blood samples. The results will be returned electronically via a password-protected encrypted database and transcribed to the main study database.

The data will be archived according to the Sponsor's standard operative procedure.

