7.2 Sampling

7.2.1 Size of sample

50 participants will be recruited.

The average value for serum neurofilament light (NFL) in a large sample of healthy controls was 22.9pg/ml (IQR 16.8-31.4) (Disanto G, Barro C, Benkert P, et al. Serum neurofilament light: a biomarker of neuronal damage in multiple sclerosis. *Annals of neurology*. 2017 Jun;81(6):857-70).

Using a sample of size of 50 allows an effect size of 0.46 on serum NFL levels to be detected with power 0.9 and type 1 error rate of 5%.

This sample size allows a relatively small change in serum NFL levels to be detected but as we do not know whether all CO exposed patients will have raised levels and we will have a range of levels of exposure, this sample size will allow us to explore these issues.

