7.2.2 Sampling technique

A convenience sampling technique will be employed with participants identified via a National NHS clinic at St George's Hospital, London that assesses and treats patients with previous CO exposure. All participants will have confirmed exposure to CO and individuals with only suspected exposure will not be included. If eligible for participation, patients will be provided with an information leaflet and asked if they would like to participate. Any individual with confirmed CO exposure can be referred into this clinic nationally. It is also linked to an on going study, the EDCO study (IRAS 248936), which is screening individuals for carbon monoxide exposure in emergency departments. Individuals identified as having been exposed to CO from this study will be offered a follow up in this clinic. This sampling technique has been used to optimise recruitment given the fact CO exposure is relatively rare.

Cognitive and blood biomarker assessment after CO Exposure

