7.2.3 Biological Sample Handling

Sample collection

Two samples of 4-5ml each to be collected from each participant:

- Serum (gel tube). One 10 or 7mL tube
- Plasma(EDTA-K2 tube, purple cap). One 10 or 7mL tube

Processing at St George's lab

Tubs will be mixed by turning up and down 8-10 times. The serum sample will be allowed to coagulate for >30 min.

Serum:

After coagulation, it will be centrifuged at 2500 x g for 20 minutes with temperature set at +4°C.

Plasma:

It will be centrifuged at 2500 x g for 20 minutes with temperature set at +4°C.

Aliquotation and storage

0.5-1.0 mL aliquots of the samples will be pipetted into cryotubes.

All tubes will be labelled (patient unique studyID, date etc.) and frozen immediately at -80°C.

Cognitive and blood biomarker assessment after CO Exposure

Samples will be stored at St. George's Hospital until all samples have been collected. Samples will then be sent in bulk by specialist courier to the UK Dementia Research Institute at UCL ([name]'s Group) to test for neurological blood biomarkers. Upon completion of sample analysis, remaining sample material will be disposed in accordance with the Human Tissue Authority's Code of Practice.

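### The primary biomarker comparison rests on a healthy-control database whose source, size, age and sex content and specimen type are not fixed, and the test behind the sample size is not stated

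*Protocol*

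**What the plan says.** Protocol 4.1 sets the primary aim: "To determine whether blood biomarkers sensitive to neuronal injury are elevated in the sub-acute to chronic period" after confirmed CO exposure. Every participant is exposed, so whether levels are raised can only be judged against an outside reference. Section 5.1 supplies it in one sentence: "Blood tests will also be compared to a database of healthy controls to identify changes in these biomarkers after CO exposure". It says nothing on where the database comes from, how many people it holds, whether it carries age and sex, which specimen was assayed, or in which laboratory. For the cognitive side the wording is a little fuller: "Cognitive tests and questionnaires will be compared to those from large normative control databases". No size is claimed for the blood database.

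Three markers need a reference: "Blood biomarkers will include NfL, tau and glial fibrillary acidic protein". Both serum and plasma are collected; 7.2.3 (Biological Sample Handling) lists a serum gel tube and "Plasma(EDTA-K2 tube, purple cap). One 10 or 7mL tube".

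On recruitment, 7.2.2 (Sampling technique) says: "A convenience sampling technique will be employed with participants identified via a National NHS clinic". The only age limit is the exclusion of those under 18 (7.1.2), and no matching is described. Section 8.6 records participants' age and gender.

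Section 7.2.1 (Size of sample) cites a published reference: "The average value for serum neurofilament light (NFL) in a large sample of healthy controls was 22.9pg/ml (IQR 16.8-31.4"). It then states: "Using a sample of size of 50 allows an effect size of 0.46 on serum NFL levels to be detected with power 0.9", with a type 1 error rate of 5%. It gives no test, no sidedness and no number of controls, and it does not say that the published sample is the comparison database of 5.1.

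**The concern.** With no internal control group, the choice of comparator largely decides what the primary result means. Any difference between clinic patients and database members in age, sex, specimen or laboratory enters the estimate alongside the effect of CO. The effect the study is sized for is modest, so a modest imbalance could produce it or hide it. Model details can wait for an analysis plan, but the content of the database cannot: if the set finally chosen lacks age and sex, no later plan can adjust for them.

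The second issue is power. The sample-size figures look like a comparison with a known constant, whereas 5.1 plans a comparison with people whose mean has its own sampling error. If the database is small, power 0.9 would not hold.

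**Working it through.** **Inputs from the protocol:** 50 patients, effect 0.46 SD, power 0.9, type 1 error 5%, control NfL 22.9 pg/ml with IQR 16.8 to 31.4. **Assumed, because the protocol gives none:** number of controls, age gap, change in NfL per year of age, age SD.

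**1. Reproducing the stated figure.** Two-sided test against a fixed value, normal approximation:
- n = ((1.960 + 1.282)/0.46)² = (3.2415/0.46)² = 49.66, rounded up to 50.
- Detectable effect at n = 50: 3.2415/√50 = 0.458.
- The exact t version gives power 0.890 at 0.46.

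So the arithmetic is sound under this reading. The standard error is 1/√50, with nothing for the controls.

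**2. Other readings.** A two-sample test has standard error √(1/50 + 1/m) for m controls.
- One-sided 5%: power 0.90 at 0.46 needs 1/m = (0.46/2.926)² − 1/50 = 0.00471, so m ≈ 212.
- Two-sided 5%: 1/m = (0.46/3.2415)² − 1/50 = 0.000138, so m ≈ 7,200 for a full 0.90.

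The protocol states neither.

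**3. Two-sample power at 0.46 SD, 50 patients, 5% (t test).**

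| Controls (assumed) | Two-sided | One-sided |
|---|---|---|
| 50 | 0.62 | 0.74 |
| 100 | 0.75 | 0.84 |
| 250 | 0.84 | 0.91 |
| 500 | 0.87 | 0.93 |
| 1000 | 0.89 | 0.94 |

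**4. Size of the planned effect.** Log-SD = ln(31.4/16.8)/1.349 = 0.464. The two halves of the IQR give log-SDs of 0.468 and 0.459, so the log scale is close to symmetric. Then 0.46 × 0.464 = 0.213, and exp(0.213) = 1.24. The design is sized for a ratio of about 1.24.

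**5. Effect of an imbalance not due to CO (illustration).** Suppose patients are 5 years older than controls and NfL rises 1% or 2% per year. The shift is 5 × ln(1.01)/0.464 = 0.107 SD, or 5 × ln(1.02)/0.464 = 0.214 SD. With no CO effect, the two-sided unadjusted test rejects with probability:
- 250 controls: 0.11 or 0.28
- 500 controls: 0.11 or 0.30
- 1000 controls: 0.12 or 0.31

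Rejection rises slightly with more controls, because the bias stays fixed while the standard error shrinks. If patients are instead 5 years younger, power for a true 0.46 SD with 250 controls falls from 0.84 to 0.62 or 0.35. In simulation (4,000 runs, 50 against 250), adjusting for age brought false positives back to 4% to 5%.

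**6. What adjustment does to power.** With an assumed age SD of 15, age explains (ln(1.01) × 15/0.464)² = 0.10 or (ln(1.02) × 15/0.464)² = 0.41 of log-NfL variance. Power with no age gap, at effect 0.46/√(1 − R²):

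| Controls (assumed) | 1% per year | 2% per year |
|---|---|---|
| 50 | 0.67 | 0.84 |
| 100 | 0.80 | 0.93 |
| 250 | 0.88 | 0.97 |
| 1000 | 0.92 | 0.99 |

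**The case against.** The strongest reply has four parts.

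*The power figure may be right.* The aim is directional, and a one-sided two-sample test with about 212 or more controls also gives 0.90. The only healthy-control set the protocol describes is called large, and with 1000 controls the two-sided loss is about 0.01. This stands. A reader might infer that the sample size is miscalculated or that 50 patients are too few. The document supports neither: it shows an unstated test, not an arithmetic error.

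*The confounding premise is not in the document.* No section says that these markers vary with age, sex or laboratory, and the slopes and age gap in step 5 are assumed. This stands as a limit on the size. The point itself needs only that an unmatched clinic sample and an unspecified database could differ by 0.1 to 0.2 SD for some reason other than CO.

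*Adjustment belongs in an analysis plan.* This stands in part. A reader might infer that the analysis will be unadjusted, but the protocol does not say so, and covariates and model form are commonly settled later. Which comparator is used, and whether it holds age and sex, is a design choice that a later plan cannot repair.

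*The cost may be understated.* Nothing shows that a suitable control set exists for all three markers. This stands, and it is a reason to settle the source early.

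**Conclusion.** The point holds and should be fixed; it does not stop the study. The primary answer rests on a comparator that the protocol leaves undefined, with no internal controls and no matching. Under an assumed non-CO difference of 0.11 to 0.21 SD, false positives would be about 11% to 31% with 250 to 1000 controls, and a larger database would not help. The same difference in the other direction could hide a real effect. These rates illustrate sensitivity and do not predict what will happen.

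The power issue is secondary and conditional. The fixed-value reading fits the stated figures closely but is inferred. On a two-sided test the loss is material with 50 or 100 controls (0.62, 0.75), moderate with 250 (0.84) and small with 1000 (0.89). All figures concern NfL, since the protocol gives no control values for tau or glial fibrillary acidic protein (GFAP).

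**What to change.** **In 5.1, before the batch assay:**
- Name the control source and its size, and say whether it is the sample cited in 7.2.1 (Size of sample).
- Require individual age and sex (or age-specific norms), the same specimen type as the study assay and, where available, the same laboratory.
- Make the primary comparison log NfL between patients and controls, adjusted for age and sex.
- Make tau and GFAP secondary, or put all three under a stated multiplicity rule. Three co-primary tests would not be covered by a power statement for NfL at 5%: with a Bonferroni split (5%/3), two-sided unadjusted power at 0.46 SD would be 0.71 with 250 controls and 0.78 with 1000.

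**In 7.2.1 (Size of sample):** state the test and sidedness behind 0.46, and restate power as a two-sample figure for the actual number of controls.

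Details of the correlation analyses can be left to the analysis plan.

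**Cost:** no extra patients, visits or samples. Participants' age and gender are already recorded, and the samples are stored and assayed together at the end, so the comparator can be fixed before any biomarker result exists. The choice of database is narrowed, and finding one that qualifies may take effort. The stated power may fall slightly below 0.9. Adjustment may recover some or all of that, depending on the number of controls and how strongly age predicts NfL; on the assumptions in step 6, 100 controls at 1% per year would still give only 0.80.

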7.1 Eligibility Criteria

50 individuals with confirmed evidence of CO exposure will be recruited. This will allow assessment of common sequelae after CO exposure.

7.1.1 Inclusion criteria:

- Individuals identified as having confirmed exposure to CO between 2 weeks to 2 years at time of assessment. CO exposure determined by either;
 - documented COHb levels above 1.6% in non-smokers and above 6.3% in smokers.
 - or, individuals with evidence of being exposed to raised levels of CO and symptoms

7.1.2 Exclusion criteria:

- age <18 years
- actual or suspected smoke inhalation
- significant neurological or psychiatric illness prior to CO exposure
- inability to provide consent

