8.6 Data protection and patient confidentiality

All data will be handled in accordance with the Data Protection Act 2018 (UK implementation of the EU General Data Protection Regulation (GDPR)).

Consent forms will be the only data collected during the study that will contain patient identifiable data. Once completed these will be stored in a locked filing cabinet in a locked office only accessible to delegated members of the research team.

Any Case Report Forms (CRFs) will not bear the participant's name or other directly identifiable data. The participant's trial Identification Number (ID) only, will be used for identification. The Subject ID log can be used to cross reference participant's identifiable information. The Subject ID log will be password-protected and stored on the St George's Hospital servers. It will only be accessible to delegated members of the research team.

Clinical data including cognitive testing and behavioural questionnaires will be uploaded to a password-protected database with the participant's unique identifier. Clinical data will also include details of CO exposure (i.e. COHb levels), other medical history and medication history. Basic participant demographic data (e.g. gender, age, medical history) will also be recorded. Blood samples will be sent to the laboratory at UCL with no patient identifiable data and results will be sent back via secure email, again with no patient identifiable data. These results will be uploaded to the database. The database will be held on the St George's Hospital IT infrastructure and will only be accessible to delegated members of the research team. The data will be kept for 10 years after the study and then deleted.

Data will be analysed at both St George's Hospital and also at St George's University of London. Data will be transferred electronically via encrypted password-protected files to the University with no patient identifiable data (just the unique study identifiers).

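### Patients who may have other illness are compared with external healthy controls and differences are read as changes after CO exposure, so other illness may contribute, most clearly to the questionnaire results

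*Protocol*

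**What the plan says.** Protocol section 5.1 (Methods) sets the comparators. For the biomarkers: "Blood tests will also be compared to a database of healthy controls". The stated purpose is to find what has changed in the markers since exposure. For the other outcomes: "Cognitive tests and questionnaires will be compared to those from large normative control databases"; the same sentence calls the comparison group healthy controls. There is no concurrent unexposed group.

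Section 7.1.2 (Exclusion criteria) fixes how healthy the patients must be. Apart from smoke inhalation, the only health-related exclusion is "significant neurological or psychiatric illness prior to CO exposure". The study summary is looser still: it lists a neurological condition and leaves out psychiatric illness. Patients are a convenience sample from a specialist clinic (section on sampling technique) and are assessed 2 weeks to 2 years after exposure.

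The protocol collects the relevant history. The section on the data collection tool puts medical and drug history on the case report form, and section 8.6 confirms it: "Clinical data will also include details of CO exposure (i.e. COHb levels), other medical history and medication history". The analyses outlined in section 5.1 are the comparisons with controls and a correlation between biomarkers and cognitive or behavioural scores. None mentions this history.

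**The concern.** One side of each comparison is described as healthy. The other side is required only to be free of significant neurological or psychiatric illness before exposure. A clinic patient with, say, a long-term heart, lung or joint condition is eligible, and so is one whose illness began between exposure and assessment. The protocol nevertheless reads the contrast as what changed after CO.

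The questionnaires are the most exposed. They cover quality of life, fatigue and return to work, among other domains, and general ill health lowers these whether or not CO did harm. If other illness is more common in the patients than in the reference group, part of the resulting deficit would be reported as a consequence of CO. The same would hold for the primary biomarker comparison, but only if some permitted illness or medication shifts NfL, tau or glial fibrillary acidic protein.

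**Working it through.** **Inputs from the protocol (section on size of sample).** Sample size: "50 participants will be recruited". Detectable effect on serum NfL: 0.46, at power 0.9 and a 5% type 1 error rate, with the test and its sidedness not stated. Healthy reference for NfL: 22.9 pg/ml, IQR 16.8 to 31.4.

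**Inputs that are assumptions.** The protocol gives neither the share of patients with other illness nor the effect of such illness on any outcome. Both are assumed below and shown as ranges. The controls are taken to carry none of this illness, which is the least favourable case.

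**Step 1: reproduce the plan's figure.** One-sample two-sided z-test against a fixed reference mean:

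n = ((1.960 + 1.282) / 0.46)² = 49.7, so 50; power at n = 50 is 0.902.

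The stated figure is reproduced and is not in dispute. With a one-sample t-test the power is 0.890. From the quoted IQR, the SD of log NfL is ln(31.4/16.8) / (2 × 0.6745) = 0.464. An effect of 0.46 SD is therefore a ratio of exp(0.46 × 0.464) = 1.24, or about 22.9 to 28.3 pg/ml.

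**Step 2: shift from other illness with no CO effect (any outcome, in SD units).** Mean shift = share ill × shift in those who are ill.

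- Lowest: 0.20 × 0.3 = 0.06 SD
- Middle: 0.30 × 0.5 = 0.15 SD
- Highest: 0.40 × 1.0 = 0.40 SD

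Chance of a significant result, one-sample t-test, n = 50, two-sided 5%:

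| Shift (SD) | Chance |
|---|---|
| 0.06 | 0.070 |
| 0.15 | 0.180 |
| 0.20 | 0.284 |
| 0.30 | 0.548 |
| 0.40 | 0.792 |

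**Step 3: the same question for NfL, on the log scale.** Let a share q of patients have an illness that multiplies NfL by r. The shift is q × ln(r) / 0.464 SD, and the variance gains q(1 − q) × ln(r)². The chance of a significant elevation (nominal 2.5% in the upper tail) is:

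| q | r | Shift (SD) | Chance |
|---|---|---|---|
| 10% | 1.25 | 0.05 | 5% |
| 20% | 1.5 | 0.17 | 21% |
| 30% | 1.5 | 0.26 | 41% |
| 30% | 2.0 | 0.45 | 74% |
| 40% | 2.0 | 0.60 | 93% |

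Nothing in the protocol supports any value of r above 1 for the illnesses it allows. This table shows only what would follow if such an effect existed.

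**Step 4: cost of restricting the patients.** If 20-40% are left out, 50 × 0.8 = 40 or 50 × 0.6 = 30 remain. One-sample t power at 0.46 is 0.89 at n = 50, 0.81 at n = 40 and 0.68 at n = 30.

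**The case against.** Five points can be made against the concern.

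- **Silence is not a defect.** A reader might infer that the recorded history will never be used. The document does not support that. Section 5.1 is a short outline that names no test, model or covariate, and a statistical analysis plan, not shown, could provide for a restricted or adjusted analysis. What stands is what the protocol does fix: the comparator, the eligibility rule and the reading of differences.
- **Healthy is undefined.** A reader might infer that the control sources exclude all long-term illness. The protocol does not describe their screening. If they exclude mainly neurological illness, much of the mismatch disappears. This stands, and it is why the size is unknown.
- **The biomarkers may be little affected.** The conditions that the protocol links to raised levels are head injury and neurodegenerative disease. All are neurological, and section 7.1.2 already excludes significant prior illness of that kind. No statement in the protocol says that other illness or medication shifts the markers. This stands: a claim that the primary comparison is biased would go too far. The exclusion of significant prior psychiatric illness likewise gives some protection to the depression and anxiety scores.
- **The magnitude is assumed.** A range of 7% to 79% runs from near nominal to severe. The 0.46 benchmark is given for serum NfL alone and says nothing about the questionnaires. Both stand.
- **Restriction can itself mislead.** Applied to all recorded history, it could remove patients whose illness or medication followed from CO and so bias towards no effect. This stands and shapes the fix.

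None of this removes the problem for quality of life, fatigue and return to work, where the effect of general illness needs no outside evidence.

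**Conclusion.** The point holds in a limited form. The comparison set out in section 5.1, with the eligibility rule in section 7.1.2, does not by itself separate CO from other illness that patients are allowed to have. This is firm for quality of life, fatigue and return to work, to the extent that the reference groups are healthier than the patients. For NfL, tau and glial fibrillary acidic protein it is conditional on an effect that the protocol does not claim.

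The shift of 0.06-0.40 SD and the 7-79% rejection rate rest wholly on an assumed 20-40% share, an assumed 0.3-1.0 SD effect and controls free of such illness. They show that the problem could be anything from trivial to serious; they do not estimate it. The sample-size statement is unaffected.

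**What to change.** In section 5.1, add a sensitivity analysis that repeats the questionnaire comparisons and the primary biomarker comparison in patients whose pre-exposure medical and medication history meets the health criteria of the control source, where those criteria are available. Name each source and its criteria; where none can be obtained, say so.

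Restrict on pre-exposure history only. Illness or medication that began after exposure must not lead to exclusion, since it may be a consequence of CO.

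Report the full and restricted estimates side by side with confidence intervals. Where the restricted estimate is materially smaller, word the conclusion as a difference from healthy controls, not as a CO effect. State beforehand what counts as materially smaller, and judge it on the estimates and intervals. Loss of significance in the smaller set is not evidence of confounding.

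The cost is a short addition to the text and one further run of each comparison on history already collected. The case report form must also show whether each condition or medication preceded exposure, which the protocol does not say it does. The restricted set is less precise: on the assumed 20-40% exclusion, power at 0.46 falls from 0.89 to 0.81 (n = 40) or 0.68 (n = 30). It should therefore remain a sensitivity analysis, with all 50 patients in the main one.
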